## Study Protocol

The Investigators retrospectively analyzed data of all patients treated at our referral Center for moderate to critical AP, as classified by Determinant-Based Classification of Acute Pancreatitis Severity (DBC). Patients treated with interventional or surgical procedures after 4 weeks (late phase) were included in the study, while patients who had undergone conservative treatment, or who has been operated within 4 weeks (early phase) were excluded from the data analysis.

The cohort sample was divided into four groups, according to the first type of the interventional or surgical management performed: percutaneous drainage group (PD), endoscopic approach group (END), surgical internal derivation of WON group (INT), and surgical necrosectomy group (NE). In all cases, the decision to intervene with an invasive procedure was taken on the basis of a clinical course not responsive to conservative management, signs of sepsis due to infected necrosis, or persistent gastric output obstruction with large fluid collections. The operative approach was chosen based on our experience and on the current Literature evidence, using a “tailored” *step-up* approach.

The acute pancreatitis severity was retrospectively graded according to the DBC, based on data drawn from clinical records.

All the procedures had been performed by surgeons, gastroenterologists/endoscopists, or interventional radiologists who composed the multidisciplinary group.

In performing primary PD, catheters up to 16 Fr were inserted using Seldinger technique, guided by ultrasound (US) or Computer Tomography (CT).

In the END approach, a lumen apposing HOT AXIOS™ (Boston Scientific, Boston, MA, USA) 15 x 10 mm metal stent was placed trans-luminally by echo-endoscopic guidance, under conscious sedation. The procedure was completed with the insertion of a naso-cystic catheter to facilitate liquefaction of debris. Further endoscopic sessions and trans-luminal necrosectomy were considered case by case.

Surgical internal derivation throughout gastric or enteric breach, adopted since 2014, was considered in the case of WON with mature walls. When the WON was not adjacent to the stomach or showed necrosis in its inferior portion, the enteric Roux-en-Y derivation was selected. However, in the vast majority of cases, trans-gastric necrosectomy and internal derivation were carried out. Firstly, a US-guided anterior gastrotomy was performed. Then, large communication up to 80 mm was created between WON and the posterior gastric wall using a mechanical stapler; finally, the necrotic debris was removed from the WON' cavity. At our Center, since 2017, a minimally invasive variant of this

approach has been performed using the da Vinci Xi robot (Intuitive Surgical Inc., Sunnyvale, CA, USA).

The NE was performed either in case of failure of endoscopic/percutaneous drainage or as a first-line treatment. It was accomplished by standard trans-peritoneal laparotomy and continuous post-operative lavage or by retroperitoneal US-guided mini-laparotomic approach, depending on the distribution of the necrotic tissue. When it was applicable, the infra-mesocolic approach was preferred. The standard trans-peritoneal NE was performed in a supine position. The retroperitoneal US-guided mini-laparotomic approach was performed in lateral decubitus: the US-guidance allowed to perform a focused right or left flank mini-laparotomy, and to obtain complete debridement using long instruments, through the retroperitoneal way.

The following variables were evaluated: sex, age, severity of inflammation according to the DBC classification, PA etiology, CT scan severity index according to Balthazar criteria, clinical prognostic score using bedside index of severity of acute pancreatitis (BISAP) score.

Total length of hospitalization, operative management, necrosis cultures, total and post-interventional Intensive Unit Care (ICU) were also recorded and analyzed together with the in-hospital morbidity, mortality and re-admissions.

Patients were checked after discharge within 14 days and followed monthly as outpatients by gastroenterologists. A CT scan was performed within 4 months, or before in case of recurrent symptoms. During the follow-up, the English Standard Short Form 36 (SF-36) questionnaire was used to evaluate the general quality of life at three and six months, one and two years. The SF-36 examines 8 areas consisting of social and physical function, physical and emotional well-being, bodily pain, vitality, mental health and overall general health perception. At the six-month follow-up, the patients also completed a specific questionnaire about the pancreatic function [10]. In particular, the total score takes in consideration abdominal pain using visual analogue pain score, diarrhea, unintentional weight loss, new onset of diabetes and use of enzyme supplementation. The score ranges between zero to five (all symptoms present).

The work has been reported in line with the STROCCS criteria.

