### *Statistical analysis*

For the data analysis, the Chi-square test was used to define associations between categorical factors and surgical groups. Continuous variables with normal distribution were expressed as mean  $\pm$  standard deviation (SD) and compared using the ANOVA test. Variables with an abnormal distribution were expressed as median and compared using the Kruskal-Wallis Test. A p-value  $\leq 0.05$  was considered

statistically significant. The statistical analysis was performed using SPSS (Statistical Production and Service Solution for Windows, SPSS Inc., Chicago, IL, USA), version 24.

All procedures performed in studies involving human participants were in accordance with the ethical standards of the institutional and/or national research committee and with the 1964 Helsinki declaration and its later amendments or comparable ethical standards. For this type of study, formal consent is not required

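### Does the undefined word *operated* in the exclusion clause leave patients drained early and treated again late without a settled status?

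*Protocol*

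**What the plan says.** One sentence of the Protocol's Study Protocol section sets eligibility. The inclusion half reads "Patients treated with interventional or surgical procedures after 4 weeks (late phase) were included in the study". The exclusion half has two limbs: "while patients who had undergone conservative treatment", and then "or who has been operated within 4 weeks (early phase) were excluded from the data analysis". The source population is "data of all patients treated at our referral Center for moderate to critical AP".

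The next paragraph forms the four groups (PD, END, INT, NE) "according to the first type of the interventional or surgical management performed". Shortly after that list it says "The operative approach was chosen based on our experience and on the current Literature evidence", and describes a tailored step-up strategy. Later in the section, necrosectomy is described both as a first-line treatment and as a treatment after failed drainage.

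Under Statistical analysis, "the Chi-square test was used to define associations between categorical factors and surgical groups". The outcomes sentence in the Study Protocol section says "Total length of hospitalization, operative management, necrosis cultures, total and post-interventional Intensive Unit Care (ICU) were also recorded and analyzed", together with in-hospital morbidity, mortality and re-admissions.

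The protocol does not define *operated*, does not give the day from which the 4 weeks run, and does not say whether the first procedure means the first ever or the first after week 4.

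**The concern.** The inclusion half names two kinds of treatment, interventional and surgical. The exclusion half uses a single word that in ordinary use suggests surgery. Taken literally, the exclusion would then act unequally. Early surgery removes a patient whatever follows. Early drainage does not, provided that another procedure was done after week 4. Such patients are plausible, because a step-up strategy produces sequences of procedures and a referral center may receive patients already drained elsewhere.

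At stake is the composition of the groups, which are the only comparison factor in the Statistical analysis section. If early-drained patients were kept and labelled by their first-ever procedure, PD and END would take in patients selected because drainage had not been enough, and INT and NE would not. That would count against the two drainage groups on further procedures and possibly on total stay. If they were kept and labelled by their first late procedure, some would move to NE instead. Two analysts could in principle build different cohorts from the same records.

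**Working it through.** The protocol states no sample size or event count, so there is no figure of its own to reproduce. The check is to apply the clauses to each type of patient under both readings of *operated*, taking an exclusion to override an inclusion.

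| Treatment history | Surgery-only reading | Any-procedure reading |
|---|---|---|
| Conservative only | out | out |
| Late procedure(s) only | in | in |
| Early surgery, with or without a late procedure | out | out |
| Early drainage, nothing late | not in (inclusion not met), but named by no exclusion | out, named by the exclusion |
| Early drainage, then a late procedure | in | out |

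Only the last row changes cohort membership.

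**Which reading fits the text better.**

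- The sentence sorts patients by treatment and timing, and the two phase labels in brackets are parallel: late procedures in, early ones out.
- The fourth row shows that the surgery-only reading leaves one type of patient in no named category. The any-procedure reading places everyone.
- The phrase about the operative approach follows directly on the grouping of all four modalities and the reasons for intervening. The Statistical analysis section calls all the comparison groups surgical. The authors' operative vocabulary therefore covers drainage and endoscopy.
- Against this, the same paragraph joins interventional and surgical with *or*, which keeps them apart. That separates two kinds of treatment but does not define *operated*.

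**Size on the unfavourable reading.** Two conditions are needed together: *operated* means surgery alone, and the first procedure means the first ever. Let r be the share of late-drained patients who need a further procedure, and s the share of PD and END made up of early-drained entrants. Neither is in the protocol; both are assumed. Early-drained entrants have a further procedure with probability 1, because the inclusion clause requires a late one.

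- Observed share = (1 − s) × r + s × 1 = r + s(1 − r).
- Rise = s(1 − r).

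| r | s = 10% | s = 20% | s = 30% |
|---|---|---|---|
| 20% | 28% | 36% | 44% |
| 30% | 37% | 44% | 51% |
| 50% | 55% | 60% | 65% |

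The smallest rise is 0.10 × 0.50 = 5 points and the largest is 0.30 × 0.80 = 24 points. On the any-procedure reading s = 0 and the rise is 0. If the first procedure means the first late one, the formula does not apply: an early-drained patient debrided late is counted in NE, and one drained again late need not have anything further after that index procedure.

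**Mortality.** Selection on surviving to week 4 might seem to favour PD and END. It does not do so by itself. Every included patient, in every group, had a procedure after week 4 and so was alive then. The condition is common to all four groups, and the protocol gives no basis for a direction on mortality.

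**Time origin.** Whatever day the 4 weeks are counted from, the same cut-off is stated for all modalities. A different origin can move individual patients across the boundary, but nothing in the protocol shows that it would do so differently by group.

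**The case for a change.** The strongest case for a change is that eligibility belongs in the protocol and cannot be left to a statistical analysis plan. The text supports more than one reading, and a single record (drained early, debrided late) can end in PD or END, in NE, or outside the cohort. A few sentences and a check of procedure dates would settle it.

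Part of this stands. *Operated*, the time origin and the meaning of *first* are undefined, and the intended reading is inferred from usage. The remark that members of the multidisciplinary group performed all the procedures suggests that the center's own procedures are meant, but it does not settle what happens with drainage done earlier at another hospital.

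What does not stand is the step from loose wording to a biased comparison. The two readings are not evenly supported: the structure of the sentence and the vocabulary elsewhere point the same way. The harmful case needs a second unproven reading on top of the first, and then shares that the protocol does not give. The outcome that would move most, the share with a further procedure, is not named as an outcome; the protocol lists operative management only in general terms. Grouping by first procedure already keeps patients whose late drainage fails, and who then have necrosectomy, in their PD or END group, so no new rule is needed for them.

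**Conclusion.** No change to the plan is called for. This is a gap that analysts fill sensibly: on the better-supported reading any invasive procedure before week 4 excludes the patient, every treatment history has one status, and the effect on the comparison is zero. A rise of 5 to 24 percentage points in further procedures in PD and END would need the surgery-only reading, the first-ever reading, and the assumed ranges of 10% to 30% for s and 20% to 50% for r, all at once. The protocol establishes none of these, and it supports no direction for mortality.

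The study is retrospective and its cohort has already been assembled, so clearer wording would record how the terms were applied; it is not shown to alter any result. The conclusion rests on an inference from the protocol's usage, since it gives no explicit definition. It would need another look if the records showed that patients with both an early drainage and a late procedure had been kept in appreciable numbers.

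### Internal derivation (INT) is dated to 2014, yet the four-group tests ignore calendar period: if any comparator was treated earlier, procedure and period are mixed

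*Protocol*

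**What the plan says.** The Study Protocol section defines the cohort broadly: "The Investigators retrospectively analyzed data of all patients treated at our referral Center for moderate to critical AP". It then narrows it by time since onset: "Patients treated with interventional or surgical procedures after 4 weeks (late phase) were included in the study". No calendar start or end appears in the text available.

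Groups are formed by what was done first: "The cohort sample was divided into four groups, according to the first type of the interventional or surgical management performed". Allocation was a clinical choice: "The operative approach was chosen based on our experience and on the current Literature evidence". One group has a stated start year: "Surgical internal derivation throughout gastric or enteric breach, adopted since 2014, was considered in the case of WON with mature walls". A robotic variant of INT is dated to 2017. PD, END and NE have no stated start.

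The list of patient variables begins: "The following variables were evaluated: sex, age, severity of inflammation according to the DBC classification". It goes on to etiology, CT severity index and BISAP, and year of treatment is not on it. The Statistical analysis section says that "the Chi-square test was used to define associations between categorical factors and surgical groups", with ANOVA or Kruskal-Wallis for continuous variables. It names no covariate, stratum or regression.

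**The concern.** One of the four groups could not exist before 2014. If the other three reach further back, part of each comparator group is non-concurrent with INT. Group membership then carries information about period, and none of the named tests can separate the two.

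What is at stake is how an INT difference is read. Better general care over time would make INT look better than it is. Referral of sicker patients in later years would make it look worse. The tests as written would not show the reader that either had happened.

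The absence of study dates is not itself the concern. The concern is that the stated method takes no account of period although the protocol gives one group a start year.

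**Working it through.** The protocol gives no sample size, event count or dates, so there is no figure of its own to reproduce. Every input below except the year 2014 is an assumption.

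**Shift in the estimate.** Let s be the share of each comparator group treated before 2014 (taken as equal in PD, END and NE), and let p_pre and p_post be the event risks before 2014 and from 2014 on, with no procedure effect. INT has risk p_post. Each comparator group has risk s·p_pre + (1−s)·p_post. So

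RR = p_post / [s·p_pre + (1−s)·p_post].

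For mortality falling from 20% to 10% with s = 0.3: 0.10 / (0.06 + 0.07) = 0.10 / 0.13 = 0.77.

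| Mortality before → from 2014 | s = 30% | s = 50% | s = 70% |
|---|---|---|---|
| 20% → 10% | 0.77 | 0.67 | 0.59 |
| 15% → 10% | 0.87 | 0.80 | 0.74 |
| 10% → 15% | 1.11 | 1.20 | 1.30 |
| 10% → 20% | 1.18 | 1.33 | 1.54 |

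At s = 0 the ratio is 1.00 throughout.

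**False-positive rate.** The four-group chi-square test (p ≤ 0.05) was simulated under the same null, 40,000 replicates per scenario:

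| Scenario | n per group | s = 30% | s = 50% | s = 70% |
|---|---|---|---|---|
| Mortality 20% vs 10% | 40 | about 6% | 8% | 11–12% |
| Mortality 15% vs 10% | 40 | about 5% | 6% | 6–7% |
| Morbidity 60% vs 40% | 40 | about 7% | 12% | 21% |
| Morbidity 50% vs 40% | 40 | 5–6% | 7% | 9% |
| Mortality 20% vs 10% | 20 | 4–5% | 5–6% | 7–8% |
| Morbidity 60% vs 40% | 20 | about 6% | 8% | 12% |

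Ranges cover risks moving in either direction. So the estimate can shift a good deal, while the excess of significant results stays small unless the period change and s are both large.

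**Precision cost of a period-aware analysis**, equal group sizes, INT versus one comparator:

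- Restriction to 2014 onward multiplies the standard error by √[(1 + 1/(1−s))/2]. At s = 30/50/70% this is 1.10/1.22/1.47.
- An additive group-plus-period model multiplies it by √[1 + s/(6(1−s))], which is 1.04/1.08/1.18. The model borrows the period effect from the three comparator groups and assumes it is the same in every group.
- Stratifying at 2014 gives the same INT contrasts as restriction, because the earlier stratum contains no INT patients.

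**Can restriction make matters worse?** Suppose there is no period or procedure effect. Patients suited to INT have 10% risk and others 20%; 30% are suited, and all of these are diverted to INT from 2014. Comparator risk before 2014 is 0.3 × 0.10 + 0.7 × 0.20 = 0.17, and from 2014 it is 0.20. With s = 50%, the all-patient RR is 0.10 / 0.185 = 0.54 and the restricted RR is 0.10 / 0.20 = 0.50. Restriction moves the estimate further from 1, through selection of patients for INT.

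**The case against.** The strongest objection is that the premise is not in the document. Nothing says that any PD, END or NE patient was treated before 2014, and part of the protocol, which may hold the study period, is not available. Bias also needs outcomes to have changed over time, on which the protocol gives no data. This stands, and it makes the point conditional. A reader might infer from the 2014 adoption date that the cohort does reach further back and that the INT comparison is biased. The text makes the first plausible but proves neither.

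Second, period adjustment is often left to a statistical analysis plan, the protocol does not exclude further analyses, and it claims no INT superiority. This stands in part. But the protocol has its own analysis section, every group test it names is unadjusted, and grouped tests of outcome invite comparison.

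Third, confounding by indication is the larger problem and needs no unseen dates: the approach was tailored to the patient, and INT was considered when the collection had mature walls. This is right. A period-aware analysis does not remove it and, as the diversion example shows, may enlarge it.

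Two further inferences are tempting but do not hold. A learning curve in INT is part of INT's own performance; neither restriction to 2014 onward nor a 2014 period term removes it, and a 2014 cut also does not address the 2017 robotic change. Nor can disagreement between the all-patient and restricted results serve as a test of whether a procedure effect is real. In a simulation of INT versus one comparator with 40 patients each, 15% risk throughout and s = 70%, the two risk differences were at least 10 points apart in 27% of runs and opposite in sign in about 19%, by chance alone.

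**Conclusion.** The point holds as a conditional one. The 2014 start of INT and the unadjusted tests are both in the protocol. If any comparator predates 2014, those tests cannot separate procedure from period. If inclusion began in 2014 or later, nothing needs to change.

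Over the assumed range, with s from 30% to 70% and mortality changing by 5 to 10 percentage points, the spurious RR for INT runs from 0.59 to 1.54. The actual size and direction are unknown. These figures rest on equal s in the three comparator groups and on assumed risks and group sizes; they are illustrations, not estimates for this cohort. This should be dealt with, at medium confidence.

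**What to change.** Tabulate year of first procedure by group. If inclusion began in 2014 or later, say so; that closes the point.

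If any PD, END or NE patient was treated before 2014, keep the all-patient tests and report beside them, as a sensitivity analysis, the INT comparisons limited to first procedures from 2014 onward. Where numbers allow, adjustment for before 2014 versus 2014 onward is an alternative. Give estimates with confidence intervals for both the all-patient and the period-aware results. Neither replaces the other. Describe INT differences as associations in either case, and state that confounding by indication remains and may be larger after restriction.

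The cost is one table row and one extra analysis. The four-week rule and length of hospitalization already require dates. The restricted comparison is less precise: the standard error for INT versus one comparator is about 10–47% larger if 30–70% of comparators predate 2014, against about 4–18% with adjustment. With an assumed 40 per group and s = 70%, only 40 × 0.3 = 12 patients would remain in each comparator group.

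### Does describing necrosectomy after failed drainage contradict the rule that groups patients by first procedure?

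*Protocol*

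**What the plan says.** Only the protocol is available. In its Study Protocol section, the allocation rule reads: "The cohort sample was divided into four groups, according to the first type of the interventional or surgical management performed". The four groups are then listed, and NE is introduced there as the abbreviation for the surgical necrosectomy group. Treatment was chosen "using a “tailored” *step-up* approach", so some patients are expected to move from drainage to surgery.

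Further on, the paragraph on necrosectomy begins: "The NE was performed either in case of failure of endoscopic/percutaneous drainage or as a first-line treatment". It goes on to the routes of access and patient positioning, for example: "The standard trans-peritoneal NE was performed in a supine position".

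On timing, inclusion covers interventional or surgical procedures after 4 weeks. Patients treated conservatively, "or who has been operated within 4 weeks (early phase) were excluded from the data analysis".

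Hospital stay, intensive care and other items "were also recorded and analyzed together with the in-hospital morbidity, mortality and re-admissions". The Statistical analysis section compares groups with chi-square, ANOVA or Kruskal-Wallis tests, without adjustment.

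**The concern.** NE is introduced as a group label, and the protocol later says NE was performed after failed drainage as well as first-line. If the label means the group in both places, a patient with failed drainage followed by necrosectomy belongs to PD or END under one sentence and to NE under the other.

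This would matter. In a step-up strategy, failed drainage is an outcome of starting with drainage. Moving those patients to NE would define a group by something that happened after treatment began. It would usually flatter PD and END and penalise NE, and the unadjusted tests would not correct it.

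The 4-week wording seems to open a second route. Inclusion speaks of interventional or surgical procedures, while the exclusion speaks only of patients operated on early. A patient drained in week 3 who has necrosectomy in week 5 could be kept or excluded and, if kept, might be placed in PD or in NE.

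**Working it through.** **1. The two statements side by side**

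| Place in Study Protocol | Function | Meaning of NE |
|---|---|---|
| Paragraph on the four groups | Allocates patients, by first procedure | Comparison group |
| Paragraph on necrosectomy | Describes when and how the operation was done | Operation |

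In the second paragraph NE is something performed in a supine position by a given route, which only an operation can be. Read that way, both statements are true together: the centre did necrosectomy in two circumstances, and patients were grouped by what was done first. The account of percutaneous drainage also speaks of primary drainage, which suggests that the authors kept first and later procedures apart.

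**2. Size of the distortion if the rule were broken**

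The protocol gives no group sizes, escalation rates or event rates, so there is no figure to reproduce and all inputs here are assumed: 60 drained first, 20 necrosectomy first, escalation share f, mortality after salvage mf, mortality 8% in other drained patients, and equal true mortality m in both groups.

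- By first procedure: m = f × mf + (1 − f) × 0.08.
- NE with salvage cases added: (20m + 60f × mf) / (20 + 60f). PD/END without them: 0.08.
- f = 0.35, mf = 0.30: m = 0.105 + 0.052 = 0.157. NE becomes (3.14 + 6.30) / 41 = 0.230, against 0.080; risk ratio 2.9.
- f = 0.20, mf = 0.20: m = 0.104. NE becomes (2.08 + 2.40) / 32 = 0.140; risk ratio 1.75.
- f = 0.50, mf = 0.30: m = 0.190. NE becomes (3.80 + 9.00) / 50 = 0.256; risk ratio 3.20.

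**3. Is the direction certain?**

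Let rs and rf be the event rates in drainage successes and failures, rNE the rate in first-line NE, and w the salvage share of the mixed NE group. Moving salvage cases changes the NE minus PD/END difference by

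w(rf − rNE) + f(rf − rs).

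This was evaluated with the same 60 and 20 patients over f = 0.20, 0.35, 0.50; rs = 0.10, 0.20; rf = 0.20, 0.30, 0.50; rNE = 0.20, 0.30, 0.50. Of the 3 × 2 × 3 × 3 = 54 combinations, 33 shift against NE, 18 in its favour and 3 not at all. The range is −18 to +38 percentage points.

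- Largest shift against NE: f = 0.50, rs = 0.10, rf = 0.50, rNE = 0.20, w = 30/50 = 0.6, giving 0.6 × 0.30 + 0.5 × 0.40 = 0.38.
- Largest shift in its favour: f = 0.50, rs = rf = 0.20, rNE = 0.50, giving 0.6 × (−0.30) + 0 = −0.18.

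All 18 shifts in favour of NE have rf below rNE. Step 2 cannot show this, because it fixes equal true mortality and sets salvage mortality well above 8%.

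**4. The 4-week rule**

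Take the patient drained in week 3 and operated on in week 5. If the exclusion covers drainage, the patient is out. If it does not, the first procedure was drainage and the patient is in PD. Placement in NE would need a rule based on the first *late* procedure, and the text has no such qualifier. Usage elsewhere favours the broad sense: the choice among all the invasive options is called the operative approach, and the Statistical analysis section calls the four groups, drainage included, surgical groups.

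**The case for a change.** The strongest case for a change is that the protocol uses a defined group label for a wider set of patients and never says that salvage operations stay in PD or END. Step-up treatment makes such patients certain to exist, every between-group result depends on where they go, and clarifying sentences plus a check of the coding would cost little. The 4-week wording adds a doubt that the first-procedure rule does not settle, namely whether an early-drained patient is in the cohort at all.

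The facts in this stand: the abbreviation has two uses, no sentence expressly covers salvage cases, and the exclusion is worded more loosely than the inclusion. The inference to a flaw does not. An explicit allocation rule needs no second sentence for each sequence it already covers, and nothing in the protocol shows that salvage cases were coded as NE. A further argument, that NE would be credited with survival time spent under drainage, does not help: mortality is in-hospital and no time-to-event analysis is described. Having to survive until salvage surgery would in any case work in favour of NE, and again only if the rule were broken.

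**Conclusion.** The concern does not hold as a flaw in the plan. Followed as written, the protocol places salvage necrosectomy in the group of the first procedure, and the misallocation bias is then zero. The risk ratios of 1.75 to 3.2 describe a departure from that rule under wholly assumed inputs, and even the direction is open if salvage patients do better than first-line NE patients. The 4-week wording leaves only the inclusion of early-drained patients unstated; the pairing of early with late phase and the broad use of operative and surgical point to a sensible reading. Spelling these points out would mostly restate an existing rule. The conclusion rests on reading NE in the necrosectomy paragraph as the operation, which that paragraph's own content supports, and on the investigators having coded groups by the rule that they state.

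### Hospital and ICU stay are compared across the four groups with no provision for in-hospital deaths, so unequal mortality can distort the comparison in either direction

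*Protocol*

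**What the plan says.** The cohort extends to critical disease: "The Investigators retrospectively analyzed data of all patients treated at our referral Center for moderate to critical AP". It is limited by timing ("Patients treated with interventional or surgical procedures after 4 weeks (late phase) were included in the study") and grouped by first procedure, not by randomisation: "The cohort sample was divided into four groups, according to the first type of the interventional or surgical management performed".

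The stay outcomes are in the Study Protocol section: "Total length of hospitalization, operative management, necrosis cultures, total and post-interventional Intensive Unit Care (ICU) were also recorded". The same sentence adds that they were "analyzed together with the in-hospital morbidity, mortality and re-admissions".

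The Statistical analysis section allows two routes for a continuous variable. The first begins "Continuous variables with normal distribution were expressed as mean" and leads to ANOVA. The second reads "Variables with an abnormal distribution were expressed as median and compared using the Kruskal-Wallis Test". Categorical factors go to chi-square. No exclusion, censoring, ranking or competing-event method is given for patients who die before discharge, and deaths are not removed from the cohort.

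**The concern.** ANOVA and Kruskal-Wallis take each value as a finished observation of the same quantity. A stay that ends in discharge measures time to recovery sufficient to leave; a stay that ends in death does not. If both enter the same variable, a patient who dies 5 days after the procedure ranks better on post-interventional ICU stay than a survivor who leaves ICU on day 20.

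This does little harm if deaths are rare or equally frequent in all groups. Here equal frequency cannot be assumed. The approach was tailored to the patient: internal derivation was considered for collections with mature walls, while necrosectomy was used first-line or after failed drainage. Mortality may therefore differ between groups, and a difference in median stay could then reflect deaths, recovery or both. At stake is whether a shorter or longer stay in one group can be interpreted at all.

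**Working it through.** **Figures in the plan.** There is nothing to reproduce: the protocol states no sample size, death rate or stay figure. Everything below is an illustration on assumed inputs.

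**Formula.** If a fraction p of a group dies, deaths count as completed stays, and F_S and F_D are the distributions of time to live discharge and time to death, the pooled median m solves (1 − p)·F_S(m) + p·F_D(m) = 0.5. Survivors can be identical in every group, and m still moves with p and with the timing of death.

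**Post-interventional ICU stay, assumed inputs.** Survivors: lognormal, median 20 days, log-SD 0.6, the same in all four groups. Deaths: median 5 days, log-SD 0.6. Mortality: 5% in three groups, 25% in the fourth.

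- Fourth group, m = 15.7: F_S = Φ(ln(15.7/20)/0.6) = 0.343 and F_D = Φ(ln(15.7/5)/0.6) = 0.972, so 0.75 × 0.343 + 0.25 × 0.972 ≈ 0.50.
- Other groups, m = 19.2: F_S = 0.473 and F_D = 0.988, so 0.95 × 0.473 + 0.05 × 0.988 ≈ 0.50.

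**Simulation of the same setting**, 30 patients per group, 4,000 runs, Kruskal-Wallis at 0.05, varying only the median time of death:

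| Deaths at median | Fourth group median | Other groups | Significant |
|---|---|---|---|
| 5 days | 15.8 | 19.4 | 21% |
| 10 days | 17.2 | 19.6 | 11% |
| 20 days | 20.1 | 20.2 | 5% |
| 30 days | 22.3 | 20.6 | 7% |

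With 5% mortality in all four groups, rejection stays at 4% to 5%.

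**A longer stay variable, same design.** Survivors: median 40 days, log-SD 0.5. Deaths: log-SD 0.5. Mortality in the fourth group: 25% or 35%, against 5% elsewhere.

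| Deaths at median | 25%: fourth vs others, significant | 35%: fourth vs others, significant |
|---|---|---|
| 12 days | 32.7 vs 39.0, 21% | 28.7 vs 38.9, 45% |
| 25 days | 36.0 vs 39.4, 8% | 34.3 vs 39.4, 15% |
| 40 days | 40.3 vs 40.3, 5% | 40.2 vs 40.2, 5% |
| 60 days | 44.3 vs 41.0, 7% | 46.4 vs 41.1, 12% |

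Both tables show the same pattern: a shorter apparent stay with early deaths, no effect when deaths fall near the usual discharge time, and a longer apparent stay with late deaths.

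**Check on the remedies.** In the 40-day setting, ranking deaths worst gives significance in 23% to 25% of runs at 25% mortality and in 50% to 51% at 35%, almost regardless of when deaths occur. Survivors are identical here, so this is the mortality difference being detected, with the higher-mortality group ranked worse. Restricting to patients discharged alive gives 4% to 5% in every scenario, as it should when survivors are identical by construction.

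**The case against.** The strongest reply is that the protocol nowhere says deaths count as ordinary completed stays. That is inferred from the tests it names, and a separate analysis plan, not shown here, might contain a rule. This stands as to wording, and the point is therefore put conditionally. It does not remove the point: the Statistical analysis section is not silent on method. It fixes tests that have no place for a stay ended by death, and applied as written they give the distortion shown.

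A reader might also infer that the group with more deaths will always look as if it recovers faster. The documents do not support this. The protocol does not say that shorter stay will be read as recovery, and the direction depends on the timing of death, which is not given. For total hospital stay, entry only after 4 weeks makes very short values unlikely unless patients arrive late by transfer or the stay counted is a re-admission. The 12-day row above is therefore an extreme for that variable. Early truncation is most plausible for post-interventional ICU stay, which runs from the procedure.

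Mortality is analysed beside stay, so an imbalance in deaths would be visible. That is a fair mitigation, but it does not correct the stay median or its p-value.

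Finally, worst-rank scoring partly re-tests mortality, which is already an outcome. This is correct, and it is why the fix leads with a split by discharge status.

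**Conclusion.** The concern holds in conditional form. The plan compares total hospital stay and total and post-interventional ICU stay on all included patients, by tests that treat every stay as completed, in a cohort where mortality is itself an outcome. If mortality differs between groups, the comparison is distorted, with a sign that depends on when deaths occur.

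The actual size cannot be established from the protocol. Under the assumptions shown, the shift in median ranges from nothing to about 10 days (28.7 against 38.9), and the chance of a significant result with identical survivors ranges from the nominal 5% to 45%. The upper end needs 35% against 5% mortality and very early deaths. For post-interventional ICU stay at 25% against 5% mortality, the largest case is 3.6 days (19.4 − 15.8) and 21%. No primary outcome is named and stay is one of several variables, so this affects the interpretation of those comparisons and not the whole study.

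**What to change.** State how in-hospital deaths enter the stay and ICU variables, and then:

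1. Report hospital stay, total ICU stay and post-interventional ICU stay by group, separately for patients discharged alive and patients who died in hospital, next to in-hospital mortality.
2. Do not interpret a pooled stay p-value as a difference in recovery.
3. For any between-group test meant to include all patients, use Kruskal-Wallis with in-hospital deaths given the worst rank. Days alive and out of hospital or ICU over a fixed window is a possible alternative if the dates are available. It is a different measure, not an equivalent one: it also counts re-admissions and needs follow-up for deaths and re-admissions after discharge, and the protocol does not list such dates.

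The first two steps and the worst-rank test need only in-hospital mortality and the stay variables, all already recorded, so the cost is a re-tabulation and one recoding step. There are two small downsides. The survivors-only comparison conditions on survival, so it describes a selected subset that may differ between groups. The worst-rank result combines death with stay, so mortality must still be shown on its own.
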